1.6 Study Variables

A. Independent Variables, Interventions, or Predictor Variables

Bright IDEAS-YA Intervention: Bright IDEAS-YA is a manualized problem-solving skills training intervention conducted by a trainer who teaches the participant the Bright IDEAS stepwise approach to problem-solving and guides the participant through solving their own problems using the Bright IDEAS approach and worksheets. The intervention consists of six 45-minute one-on-one sessions held at the clinic/hospital, by telephone between a patient and a trainer, or via video-conference session on HIPPA compliant Doxy.me (https://doxy.me/), or another institutionally-approved telehealth platform (e.g. Rutgers Zoom, site-specific telehealth platforms). Sessions are held weekly. However, due to the changing demands of cancer treatment and side effects that sometimes cause patients to feel too ill to do a session as scheduled, we allow up to 12 weeks to complete the 6

sessions. During the first face-to-face or virtual session, participants will be introduced to the Bright IDEAS model and the participant manual that explains the approach and provides worksheets for systematically solving problems. "Bright" refers to the sense of optimism that is critical to finding constructive solutions to difficult challenges. The letters in IDEAS represent the five essential steps of the PSST problem-solving approach (see Figure 1): "I"= "Identify the problem"; "D"="Determine the options"; "E"="Evaluate options and choose the best"; "A"="Act"; and "S"="See if it worked." Sessions 2-5 involve using the model to work through challenges identified by the participant. Session 6 involves a summary of the model, discussion of how the participant can continue to use the skills learned after the sessions end, and solicitation of feedback regarding the program and the website/app. See Table 1 for overview of each session.

Table 1. Overview of Bright IDEAS-YA Intervention Sessions

1. Overview of Bright IDEAS-TA Intervention Sessions										
Session	Goals/Activities Mapping to Problem-Solving									

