1	 Establish rapport Explain general rationale for Bright IDEAS-YA approach Review the 5 steps - Identify, Define your options, Evaluate options and choose, Act, See if it worked Establish basic expectations for participation 	 Reframes stressors as challenges that can be overcome, enhancing positive problem orientation and reducing negative problem orientation. Introduces 5-step approach, building rational problem-solving skills. 								
2-5	Review homework from last session Work on a patient-identified problem using Bright IDEAS-YA worksheets Identify homework for participant to use Bright IDEAS-YA between sessions	 Apply skills systematically to personal problems encourages self-efficacy to work through challenges (positive problem orientation), builds rational problem-solving skills, reduces impulsive responding, and prevents avoidance. Homework and follow-up reduce avoidance. 								
6	 Review and reinforce the elements of Bright IDEAS-YA Elicit feedback about experience using Bright IDEAS-YA Review "relapse prevention" – continue to use skills instead of returning to prior problem-solving strategies Thank patient for their participation 	 Reviewing success fosters self-efficacy and positive problem orientation. Relapse prevention reinforces continued use of these skills to any challenge young adults encounter, including achieving normative life milestones. 								

Enhanced Usual Care Comparison Group: The Enhanced Usual Psychosocial Care group will complete surveys, receive the list of resources from the NCCN adolescent and young adult patient guildeline, ¹⁹ and receive usual psychosocial care per institutional standards. Usual psychosocial care generally consists of an initial social work consultation at the time of diagnosis, referral to necessary social resources such as transportation or financial assistance services according to patient needs, and optional supportive counseling or pastoral care if sought by the patient. Ongoing service use is determined by patient needs and preference. The standardized NCCN list of resources will be given to patients in both arms to control for awareness of young adult resources. Listed resources will include websites and organizations that provide informational (e.g., websites with information about young adult cancer treatment and side effects), emotional (e.g., young adult online support groups) and practical (e.g., transportation assistance, financial assistance) support services for young adults.

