6.0 Data Management Plan

6.1 Data Analysis

Aim 1: Efficacy of the Bright IDEAS-YA intervention vs. enhanced usual psychosocial care will be evaluated assuming repeated measures linear models, using maximum likelihood estimation (MLE) (SAS Proc Mixed).⁴⁰ All randomized participants, regardless of the extent to which they completed the intervention, will be included in intent-to-treat analysis. The benefits of this approach include: (1) all available data can be included in analyses; (2) correlation between related measures and adjusted test statistics can be estimated; (3) time varying covariates (such as school/employment status, treatment status (on treatment vs. completed), utilization of usual psychosocial care) can be incorporated into the model; and, (4) the assumptions about missing data from Missing Completely at Random (MCAR) to Missing at Random (MAR) are relaxed. Site will be included as a fixed effect. The primary hypothesis is that participants in Bright IDEAS-YA will experience greater decreases in depression and anxiety and increases in HRQOL at the 6month follow-up relative to participants in the enhanced usual psychosocial care condition. The primary endpoint will be the estimated change from baseline to 6 months in depression, anxiety, and psychosocial HRQOL (i.e., Social/Family Well-Being and Emotional Well-Being), calculated as linear contrasts of regression parameters using the main effect of time and the interaction between time and treatment group from the mixed linear model. The changes from baseline to 3 months, 12 months, and 24 months will be considered secondary endpoints. For HRQOL, we are particularly interested in 12-and 24-month followups given that changes may take longer to accrue compared with distress symptoms. Sensitivity analyses will be performed to determine the robustness of conclusions.⁴¹ Planned sensitivity analyses include: (1) analysis with and without adjusting for site; (2) per protocol analysis (excluding participants who did not complete at least 4 out of 6 intervention sessions, selected because it is expected that participants would have adequate exposure and practice with the Bright IDEAS model by four sessions); (3) adjustment for imbalance in baseline characteristics, if applicable; and (4) analysis to examine any differences by racial/ethnic subgroups.

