Aim 2: Mediation analysis will be used to evaluate problem-solving ability as a mediating variable between the intervention and each of the outcomes while also allowing for a direct effect of intervention on outcome. Specifically, bootstrap approaches will estimate the proportions attributed to the direct effect and to the effect mediated through problem-solving using the R program package mediation.⁴²

A small direct effect is expected due to a positive therapeutic effect of talking to the trainer. Problem-solving ability will be measured by the total scale score and five subscales (positive problem orientation, negative problem orientation, rational problem solving, impulsive-careless style, and avoidant style), which will each be considered individually as potential mediators.

Aim 3: Potential moderators, including sex, financial strain, baseline unmet needs, and baseline distress, will be tested individually in models including all possible interaction terms. We will allow for each moderator to interact with time, arm, and time x arm to determine if it modifies the relationship between intervention and outcomes. We consider this analysis exploratory to identify subgroups who may benefit differentially from this intervention. We expect that females and participants with greater financial strain, baseline unmet needs, and baseline distress will benefit more.

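### The per-protocol rule (at least 4 of 6 sessions) selects within the intervention arm only, so the comparison is open to selection bias of unestablished direction and is not evidence of robustness

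*Combined protocol and SAP*

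**What the plan says.** Under Aim 1, section 6.1 makes intent-to-treat the primary analysis: "All randomized participants, regardless of the extent to which they completed the intervention, will be included in intent-to-treat analysis". It then says "Sensitivity analyses will be performed to determine the robustness of conclusions" and lists four. The second is a "per protocol analysis (excluding participants who did not complete at least 4 out of 6 intervention sessions". The reason given for the cut-off is an expectation that "participants would have adequate exposure and practice with the Bright IDEAS model by four sessions". The rule names no arm, and no adherence criterion is given for controls.

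Section 1.6 describes the two arms. For the intervention arm, "The intervention consists of six 45-minute one-on-one sessions". For controls, "The Enhanced Usual Psychosocial Care group will complete surveys, receive the list of resources" and usual psychosocial care. The schedule in section 1.10 marks sessions for the intervention arm only.

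On attendance, section 1.6 mentions "side effects that sometimes cause patients to feel too ill to do a session as scheduled" and for that reason allows up to 12 weeks for the six sessions, with telephone and video as alternatives to the clinic. The plan gives no expected completion rate, and the per-protocol item says nothing about how selection of completers will be handled.

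**The concern.** A per-protocol set defined by session attendance can drop people from one arm only. Those kept in the intervention arm have selected themselves by attending, while the controls stay unselected. If attendance is related to how depression, anxiety or quality of life would have changed anyway, the two groups differ for a reason other than treatment.

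The analysis is offered as a check on robustness. A contrast that can move away from the intent-to-treat result through selection alone cannot do that job. Agreement would not confirm the primary result, and a larger effect among completers could be misread as a dose-response.

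**Working it through.** The documents give no figure for the per-protocol set, so there is nothing to reproduce. The check has a literal count and an illustration.

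**Inputs from the protocol.** 344 participants and 30% dropout (1.5); 1:1 allocation (1.3 A); planned effect 0.26 SD for depression (1.5); no sessions for controls (1.6, 1.10). Per arm: 344/2 = 172 randomised and 172 × 0.70 = 120.4 observed.

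**Assumptions, not in the documents.** Share *c* of the intervention arm completing at least four sessions; correlation ρ between completion (as a latent normal variable) and the analysed outcome; or, equivalently, the completer minus non-completer difference *g* in SD. Two-sided 5% test.

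**1. Literal reading.** All 172 controls have zero sessions and are excluded. No between-arm contrast can be estimated.

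**2. Intended reading, no true effect.** The control mean equals the mean of the whole intervention arm, c·m₁ + (1 − c)·m₀, where m₁ is the completer mean and m₀ the non-completer mean. Completers minus controls is therefore (1 − c)(m₁ − m₀) = (1 − c)·g. In latent form this is ρ·φ(z)/c, where z is the normal cut-off that leaves a share c completing.

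At c = 0.7, φ(z) = 0.348. With ρ = 0.2 the bias is 0.2 × 0.348/0.7 = 0.099 SD, or 0.099/0.26 = 38% of the planned effect. This corresponds to g = 0.099/0.3 = 0.33 SD. The standard error is √(1/84.3 + 1/120.4) = 0.142, so the chance of a significant result is Φ(0.70 − 1.96) + Φ(−0.70 − 1.96) ≈ 0.104 + 0.004 = 10.8%, instead of 5%. Simulation gives 10.8% to 10.9%.

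**3. Dependence on the assumptions.** Positive values favour the intervention.

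| Completion c | Selection assumed | Bias (SD) | Chance of a significant result, no true effect |
|---|---|---|---|
| 0.7 | ρ = 0.1 | 0.05 | 6.5% |
| 0.7 | ρ = 0.2 | 0.10 | 11% |
| 0.7 | ρ = 0.4 | 0.20 | 28–30% |
| 0.6 | ρ = 0.4 | 0.26 | 42% |
| 0.8 | ρ = 0.2 | 0.07 | 8% |
| 0.9 | ρ = 0.2 to 0.4 | 0.04–0.08 | not computed |
| 0.7 | g = 0 | 0 | 5% |
| 0.7 | g = −0.3 | −0.09 | 9.7% (9.2% against the intervention) |
| 0.6 | g = −0.3 | −0.12 | 12.7% (12.4% against the intervention) |

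**4. The endpoint is change from baseline.** With equal SDs, the bias in change is (ρ at 6 months − ρ at baseline)·φ(z)/c in units of the score SD. If completion is equally correlated with both scores, the bias cancels. The ρ in the table must therefore be read as selection on change.

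**5. Properties of the alternative.** The complier-average estimate is about the intent-to-treat effect divided by c. Its standard error is about 1/c times the intent-to-treat one: 1/0.8 = 1.25 to 1/0.6 = 1.67. If fewer than four sessions have a mean effect Δ, the estimate equals the true complier effect plus ((1 − c)/c)·Δ. At c = 0.7 that adds 0.43Δ.

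**The case against.** A reader might infer that the check is biased towards the intervention because sicker patients miss sessions. The documents do not support that as a fact. Section 1.6 speaks of sessions that cannot be held as scheduled and answers with a longer window and remote options. It does not say that ill patients end with fewer than four sessions. The endpoint is change from baseline, and under Aim 3 the plan expects that "participants with greater financial strain, baseline unmet needs, and baseline distress will benefit more", so selection could run either way. This objection stands in full.

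It can also be said that the literal reading is only a matter of wording, since the rationale for the cut-off makes the intended scope clear. That is right, and a reading that leaves no controls produces no estimate rather than a biased one. It still needs one clause of correction.

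The sizes rest on assumed completion and correlation. Model covariates such as treatment status (6.1) could absorb part of any selection. If people who drop out of the study are mostly those who stop sessions, completion among those observed would be higher and the bias smaller. This stands too: the 42% in the table is the worst corner of an assumed grid, not a forecast.

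Finally, this is one of four sensitivity analyses, and no decision rule depends on it. That limits the consequence. It does not make the completer comparison a valid check on the primary result.

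**Conclusion.** The point holds in limited form. The rule can exclude only on intervention-arm behaviour, so the intended comparison sets self-selected completers against unselected controls and loses the protection of randomisation. This follows from the text and needs no assumed number.

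Bias favouring the intervention is plausible but not established. The 0.10 SD figure rests on 70% completion and a correlation of 0.2 with the analysed outcome, neither of which the plan gives. Other assumptions in the table give anything from −0.12 to +0.26 SD, including zero. The intent-to-treat primary analysis is unaffected, so this is an inexpensive improvement and not a threat to the main conclusion.

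**What to change.** 1. State in section 6.1 that the four-session rule applies to the intervention arm only.
2. Stop presenting the unadjusted completer comparison as evidence of robustness. Drop it, or keep it labelled as open to selection bias of unknown direction.
3. As the adherence analysis, use randomised arm as the instrument and keep all randomised participants. Report two versions:
   - number of sessions attended as the exposure, assuming an effect linear in sessions;
   - a complier-average effect for at least four sessions, assuming no effect below four.

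The second version should not stand alone. Table 1 in section 1.6 has session 1 already reframing stressors and introducing all five steps, and Aim 2 in section 6.1 expects a small benefit simply from talking with the trainer. If fewer than four sessions help, the complier effect is overstated. Both versions also assume that assignment acts only through sessions. Section 1.3 A sends the manual and worksheets to the intervention arm, so this should be stated as well.

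The cost is SAP wording and one or two models on session data already collected (1.3 B). Intervals will be wider, with a standard error about 1.25 to 1.67 times the intent-to-treat one at an assumed 80% to 60% completion. The analysis estimates the effect of adherence. Its test is essentially the intent-to-treat test rescaled, so it should not be reported as independent confirmation.

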1.0 Research Design

1.1 Purpose/Specific Aims

The purpose of this project is to evaluate efficacy of Bright IDEAS, an evidence-based problem-solving skills training (PSST) program, as a supportive care intervention for adolescent and young adult (AYA) cancer patients compared with enhanced usual psychosocial care with 344 young adult patients newly diagnosed with cancer.

A. Objectives

We will evaluate the efficacy of Bright IDEAS-YA by examining changes in psychosocial outcomes from baseline to post-intervention (3 months) and follow-up (6, 12, and 24 months).

We will determine the extent to which changes in aspects of problem-solving ability mediate the intervention effects and examine relevant moderators.

B. Hypotheses / Research Question(s)

Aim 1: Evaluate the efficacy of Bright IDEAS-Young Adults on psychosocial outcomes.

Hypothesis 1: Participants who receive the Bright IDEAS-YA intervention will report lower depression, anxiety, and impairment in health-related quality of life over time than participants who receive usual psychosocial care.

Aim 2: Determine the extent to which problem-solving ability mediates treatment effects.

Hypothesis 2: The effects of the intervention will be mediated by improved positive problem orientation and rational problem-solving skills, and reduced negative problem orientation, impulsive style, and avoidant style.

Aim 3 (Exploratory): Examine moderators of treatment effects.

Sex, financial strain, and baseline unmet needs will be examined as potential moderators of treatment effects to identify subgroups who benefit most from this intervention.

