
B. Data Points

All participants will be asked to complete follow-up surveys at 3 months (post-intervention), 6 months (3-month follow-up), 12 months (9-month follow-up), and 24 months (21-month follow-up). Study staff will also collect data regarding participant completion of intervention sessions and trainer fidelity. Intervention sessions will be audio-recorded with participant permission for fidelity evaluation and trainer supervision.

C. Study Duration

The overall study will last 5 years. Each subject will participate for 2 years.

D. Endpoints

The primary endpoint will be the estimated change from baseline to 6 months in depression, anxiety, and psychosocial HRQOL (i.e., Social/Family Well-Being and Emotional Well-Being), selected to allow for examination of temporal mediation of problem-solving ability post-intervention. The changes from baseline to 3 months, 12 months, and 24 months will be considered secondary endpoints.

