1.5 Sample Size Justification

Up to 344 YA patients newly diagnosed with cancer will be enrolled across sites. There are no exclusion criteria based on gender or race. We expect the percentage of male/female and minority race participants enrolled to reflect the distributions seen at three sites.

Power focused on Aim 1 and was calculated based on effect size estimates that incorporate both estimates of change in mean as well as standard deviations from our pilot data and compared against published data, assuming an intent-to-treat analysis. For the proposed study, we assume the standard deviation will be 70% of the pilot standard deviation, due to tightening of the eligibility criteria to exclude those with cancer recurrence and recruit within 4 months of first diagnosis. In addition, we assume that the control group will see 20% of the change in depression compared to intervention. This leads to a Cohen effect size of 0.26. Assuming 344 subjects with 30% dropout, we will have 85% power to detect an effect of intervention on the Depression score. Similar calculations demonstrate 82% power to detect an effect of intervention on Anxiety. If we observe a group difference closer to 3.22 for Depression, cited as clinically meaningful in previous literature,²³ then under the assumptions listed above, our Cohen effect size will be closer to 0.29 and our power for the primary outcomes will be higher. For HRQOL, pilot Cohen estimates of effect size and estimates from the literature with the assumptions above would yield a Cohen effect size of 0.32, which would yield a power of 95%.²⁴²⁵

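### Aim 2 names no missing-data method; run as written it would use complete cases, and its total effect may then not match the Aim 1 intent-to-treat effect if distress-driven dropout differs by arm

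*Combined protocol and SAP*

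**What the plan says.** Aim 1 (section 6.1) has an explicit approach to incomplete data. It fits a repeated-measures linear model by maximum likelihood, and "All randomized participants, regardless of the extent to which they completed the intervention, will be included in intent-to-treat analysis". One listed advantage is that "all available data can be included in analyses"; another is that the missing-data assumption is MAR rather than missing completely at random. The primary endpoint is the change from baseline to 6 months.

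Aim 2, in the same section, changes estimator: "bootstrap approaches will estimate the proportions attributed to the direct effect and to the effect mediated through problem-solving using the R program package mediation". The mediators are the SPSI-R:S total and its five subscales, "which will each be considered individually as potential mediators". The Aim 2 text names no visits, covariates, analysis set or treatment of missing scores. The order, mediator at 3 months and outcome at 6 months, can be inferred only from the endpoint paragraph of section 1.3, where 6 months was "selected to allow for examination of temporal mediation of problem-solving ability post-intervention". None of the four planned sensitivity analyses in section 6.1 deals with missing data.

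Hypothesis 2 (section 1.1) states what Aim 2 is to explain: "The effects of the intervention will be mediated by improved positive problem orientation and rational problem-solving skills". Section 1.5 gives the planning figure: "Assuming 344 subjects with 30% dropout".

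**The concern.** A proportion mediated is useful here only if the direct and mediated parts add up to the effect reported under Aim 1. Nothing in the plan ensures this.

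The outcome model contains the mediator as a predictor, so a row needs both scores to contribute. With no imputation or full-information method named, the two models fitted to a common data set run on participants who have both. Aim 1 also uses the 3-month outcome of a person who then misses 6 months, so dropout that depends on 3-month distress is handled under MAR. A complete-case mediation analysis sets that person aside, 3-month score included.

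If distressed participants leave one arm more readily than the other, the complete-case total effect and its split are biased even though Aim 1 remains valid. The paper could then report a share of an effect that differs from its own primary result.

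**Working it through.** **Sample.** The plan states no sample size for Aim 2, so there is no figure to reproduce. The inputs are N = 344 and 30% dropout (section 1.5).

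344 × 0.70 = 240.8, about 241 with both scores; 344 − 241 = 103 set aside. The number is lower if different people miss 3 and 6 months, and higher if part of the 30% leaves after 6 months.

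**What each analysis estimates.** Let A be arm, M the 3-month mediator, and Y0, Y3, Y6 the outcome at baseline, 3 and 6 months.

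- Aim 2, complete cases: fit M on A and Y0 (arm coefficient a), and Y6 on A, Y0 and M (arm coefficient c′, mediator coefficient b). Mediated = ab; direct = c′; total = ab + c′; proportion = ab/(ab + c′). By least-squares algebra the total equals the arm coefficient from regressing Y6 on A and Y0 in the same rows, so Y3 plays no part.
- Aim 1, maximum likelihood with monotone dropout: predict the 3-month mean in each arm from Y0, then the 6-month mean from Y0 and that 3-month mean. Y3 enters, which corrects for dropout that depends on it.

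**Simulations.** All parameters below are assumptions; the documents give none. Baseline-adjusted models were used in sets A and E, and 30% drop out in every set. Slopes are log-odds of dropout per SD of 3-month distress (set E: per unit of simulated score).

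- A: true total −0.273 SD, 65% mediated.
- B: −0.254, 68%, 30% per arm.
- C: −0.28, 65%, 30% per arm.
- D: 77% mediated, 30% per arm.
- E: −0.26, 60%; half the dropout by month 3 (driven by Y0), half by month 6 (driven by Y3), 30% overall. Y3 = bM + direct·A + 0.45·Y0 + 0.6u and Y6 = bM + direct·A + 0.45·Y0 + 0.42u + 0.43e.

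| Dropout slopes | Set | Complete-case total against truth | Shift | Proportion mediated |
|---|---|---|---|---|
| Random | E | −0.260 / −0.261 | 0.001/0.261 = 0.4% | 60% (true 60%) |
| Same in both arms, 1 | A | −0.274 / −0.273 | 0.001/0.273 = 0.4% | 63% (true 65%) |
| Same in both arms, 1 | E | −0.250 / −0.260 | 0.010/0.260 = 4% | 59% |
| 1 vs 0.75 | C | – | 5% | 63–66% |
| 0.5 vs 0.25 | C | – | 7% | 68% |
| 1 vs 0.5 | C | – | 11% | 61–69% |
| 0.75 vs 0.25 | E | −0.290 / −0.260 | 0.030/0.260 = 12% | 56% |
| 1 vs 0.5, or 0.5 vs 0 | D | – | 11–15% | – |
| 0.5, controls only | B | −0.213 / −0.254 | 0.041/0.254 = 16% | 77% (true 68%) |
| 0.5, intervention only | B | −0.292 / −0.254 | 0.038/0.254 = 15% | 63% |
| 1, one arm only | C | – | 24–25% | – |
| 1, intervention only | E | −0.320 / −0.259 | 0.061/0.259 = 24% | 55% |
| 1, one arm only | D | – | about 27% | 65–96% over D's cases (true 77%) |
| 1, controls only | B | −0.181 / −0.254 | 0.073/0.254 = 29% | 85% |
| 1, intervention only | B | −0.325 / −0.254 | 0.071/0.254 = 28% | 58% |
| 1, controls only | A | −0.189 / −0.273 | 0.084/0.273 = 31% | 79% |
| 1, intervention only | A | −0.358 / −0.273 | 0.085/0.273 = 31% | 56% |

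A slope of 2 in the intervention arm only (set E) gives −0.362 against −0.261, or 0.101/0.261 = 39%. In every row of set E the Aim 1 estimate stayed at about −0.26.

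In these baseline-adjusted models the effect looks too small when distressed controls leave and too large when distressed intervention participants leave.

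**Noise at the trial's size.** In set E with n = 344 and random dropout, the difference between the Aim 2 and Aim 1 totals has an SD of 0.052, and it exceeds 0.05 in 34% of replicates.

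**Covariates.** In set E with change scores and no baseline covariate, the full-data proportion mediated is 26% instead of 60%. With slopes 1 vs 0 the total becomes −0.225 against −0.259, so the bias changes direction. The covariates therefore need stating too.

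**The case against.** The strongest reply is that the plan does not say complete cases. It names a bootstrap and a package, and imputing beforehand is not excluded. It also lists no covariates, so it cannot be said to have decided to ignore the 3-month outcome. Both points stand: complete-case use is inferred from the named method and the absence of any other. The silence still needs filling, because the named method followed literally leads there.

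A reader might infer that 30% dropout by itself makes Aim 2 explain a different effect from Aim 1. The documents do not support that. Random dropout, or the same process in both arms, leaves the total nearly unchanged; material bias needs outcome-related dropout that differs by arm. No passage gives evidence of this. It is only plausible: participants are told their arm (section 1.3), only one arm has six trainer sessions (section 1.6), and trainers check willingness to continue at each session (section 4.4).

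The 30% has no visit attached and follow-up runs to 24 months, so 241 is conditional.

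Sampling noise also matters. A bias of 0.03 is smaller than the chance SD of about 0.05, and 0.085 is 0.085/0.05 = 1.7 of those SDs. A single trial may not reveal the bias, but that does not remove it.

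Finally, power was calculated for Aim 1, and no efficacy conclusion depends on Aim 2. That limits the stakes. Aim 2 nevertheless has its own hypothesis and, unlike Aim 3, is not labelled exploratory.

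**Conclusion.** The concern holds in conditional form. Aim 1 has a MAR-based method using all available data; Aim 2 has no stated method and, run as written, would use about 241 of 344 if 30% are lost by 6 months. Its total effect may then not match the Aim 1 contrast. The bias in the total is 0 to 4% under random or arm-equal dropout, 5 to 16% under moderate differences between arms, and 24 to 31% in the extreme case of slope 1 in one arm only. In that extreme case the proportion mediated moves by roughly 5 to 20 percentage points (set E 60% to 55%; set D 77% to as much as 96%). Partial data are discarded whatever the mechanism.

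These sizes rest on assumed parameters and dropout models. It would go too far to say that the plan commits to complete cases, or that a mismatch is certain. Aim 1 is unaffected.

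**What to change.** In section 6.1 (Aim 2), state that:

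- mediation uses the 3-month mediator and the 6-month outcome in all randomised participants, adjusted for baseline mediator and baseline outcome;
- missing scores are multiply imputed by arm from baseline and all follow-up outcome and SPSI-R:S scores, with imputation nested with the bootstrap so that intervals for the proportion mediated are valid; or, alternatively, a path model is fitted by full-information maximum likelihood with the 3-month outcome as an auxiliary variable;
- the Aim 2 total effect is reported beside the Aim 1 6-month contrast;
- the complete-case result is kept as a sensitivity analysis.

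The cost is SAP wording, extra programming and computing time, with no new data. The result still relies on MAR, as Aim 1 already does.
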